4.2.3 Rationale for Endpoints

4.2.3.1 Efficacy Endpoints

The primary efficacy endpoint will be the ORR of ADV/HSV-tk + valacyclovir therapy and SBRT followed by pembrolizumab in patients with metastatic TNBC and metastatic NSCLC. Secondary efficacy endpoints are antitumor activity (RECIST 1.1 in addition to modified irRC), DoR, OS rate, PFS rate, and CBR.

4.2.3.2 Biomarker Research

Blood and tissue-based markers associated with response to the study treatment will be evaluated, including but not limited to T-cell cytokine profiles (IL-1, IL-2, IL-6, IL-12, IFN- γ , TNF- α , and GM-CSF), TILs, PD-1 and PD-L1 expression, effector and suppressor immunocyte populations, and mutation load.

5.0 METHODOLOGY

5.1 Entry Criteria

5.1.1 Diagnosis/Condition for Entry into the Trial

The TNBC cohort will be comprised of patients with histologically confirmed locally advanced or metastatic TNBC that has relapsed on or is refractory to 1 or more lines of standard of care therapy. Patients must have received no more than one prior line of cytotoxic therapy for metastatic disease. Taxane and anthracycline-based chemotherapy must have been received, unless contraindicated. The NSCLC cohort will be comprised of male and female patients aged ≥ 18 years with histologically or cytologically confirmed metastatic NSCLC that is

immunotherapy naïve or previously treated with a maximum of 1 immunotherapy regimen AND chemotherapy naïve or previously treated with 1 cycle of platinum-containing chemotherapy. Patients will be screened for *EGFR* and *ALK* mutation. *EGFR/ALK* mutation-negative patients and patients with *EGFR* or *ALK* genomic tumor aberrations that have failed FDA-approved targeted therapy for these aberrations will be eligible for enrollment in the study. Written informed consent is required before performing any study-specific tests or procedures. Signing of the Informed Consent Form can occur outside the 28-day screening period. All screening evaluations must be completed and reviewed to confirm that patients meet all eligibility criteria before study entry. Results of standard-of-care tests or examinations performed prior to obtaining informed consent and within 28 days prior to study entry (except where otherwise specified) may be used for screening assessments rather than repeating such tests. The investigator will maintain a screening log to record details of all patients screened and to confirm eligibility or record reasons for screening failure, as applicable.

5.1.2 Subject Inclusion Criteria

Subjects must meet all the following inclusion criteria in order to be eligible for participation in this trial:

1. Willing and able to provide written informed consent/assent for the trial.
2. Male or female ≥ 18 years of age on the day of informed consent signing.
3. Histologically confirmed locally advanced or metastatic TNBC that has relapsed on or is refractory to standard of care therapy. TNBC is defined as estrogen receptor (ER), progesterone receptor, and human epidermal growth factor receptor 2 (HER2) negative. ER and progesterone receptor negativity are defined as $<10\%$ IHC staining. HER2 test result is negative if a single test (or both tests) performed show:
 - IHC 1+ or 0
 - In situ hybridization negative based on
 - o Single-probe average HER2 copy number < 4.0 signals/cell
 - o Dual-probe HER2/CEP17 ratio < 2 with an average HER2 copy number < 4.0 signals/cell

OR histologically or cytologically confirmed metastatic NSCLC that is immunotherapy naïve or previously treated with a maximum of 1 immunotherapy regimen AND chemotherapy naïve or previously treated with 1 cycle of platinum-containing chemotherapy. *EGFR/ALK* mutation-negative NSCLC patients and NSCLC patients with *EGFR* or *ALK* genomic tumor aberrations that have failed FDA-approved targeted therapy for these aberrations will be eligible for enrollment in the study.
4. Measurable disease based on RECIST 1.1, a target lesion of suitable diameter (at least 1 cm) for SBRT with the exception of a primary breast tumor, and a non-target lesion (visceral metastatic lesion) at least 1 cm in diameter for abscopal effect evaluation.
5. Willing to provide biopsy tissues as required by the study.
6. Eastern Cooperative Oncology Group (ECOG) performance status of 0 or 1.
7. Adequate organ function as defined in Table 1. All screening labs should be performed within 28 days of trial treatment initiation.

Table 1 Adequate Organ Function Laboratory Values

System	Laboratory Value
Hematological	

Absolute neutrophil count (ANC)	≥1,500/μL (without granulocyte colony stimulating factor support within 14 days of assessment)
Platelets	≥100,000/μL
Hemoglobin	≥8 g/dL without transfusion or erythropoietin dependency (within 7 days of assessment)
White blood cell count (WBC)	>2,500/μL and <15,000/μL
Lymphocyte count	≥500/μL
Renal	
Serum creatinine	<2 X upper limit of normal (ULN)
Hepatic	
Serum total bilirubin	≤1.0 X ULN (Subjects with known Gilbert's disease who have serum bilirubin level ≤3 X ULN may be enrolled)
Aspartate transaminase (AST) and Alanine transaminase (ALT)	≤2.5 X ULN with normal alkaline phosphatase (≤5 X ULN for subjects with liver metastases) OR ≤1.5 X ULN in conjunction with alkaline phosphatase >2.5 X ULN
Albumin	≥2.5 mg/dL
Coagulation	
International normalized ratio (INR) or prothrombin time (PT)	≤1.5 X ULN unless subject is receiving anticoagulant therapy as long as PT or aPTT is within therapeutic range of intended use of anticoagulants
Activated partial thromboplastin time (aPTT)	≤1.5 X ULN unless subject is receiving anticoagulant therapy as long as PT or aPTT is within therapeutic range of intended use of anticoagulants
^a CrCl should be calculated per institutional standard.	

8. Life expectancy ≥ 6 months.
9. ≥ 4 weeks since any major surgery.
10. A 2-week washout period post any prior systemic anticancer therapy, RT, targeted anticancer therapy or mAb, and/or investigational therapy is required prior to trial entry. Subject should be recovered (i.e., ≤ Grade 1 or at baseline) from AEs due to a previously administered therapy.
 - Note: Subjects with ≤ Grade 2 neuropathy are an exception to this criterion and may qualify for the study.
11. Female subjects of childbearing potential should have a negative serum pregnancy (β-human chorionic gonadotropin [β-HCG]) within 7 days prior to receiving the first dose of the trial treatment and should not be lactating.
12. Female subjects of childbearing potential (Section 5.5.2) must be willing to use an adequate method of contraception as outlined in Section 5.5.2 – Contraception, for the course of the study through 120 days after the last dose of study medication.

Note: Abstinence is acceptable if this is the usual lifestyle and preferred contraception for the subject.
13. Male subjects of childbearing potential (Section 5.5.2) must agree to use an adequate method of contraception as outlined in Section 5.5.2 – Contraception, starting with the first dose of study therapy through 120 days after the last dose of study therapy.

Note: Abstinence is acceptable if this is the usual lifestyle and preferred contraception for the subject.

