5.1.3 Subject Exclusion Criteria

Subjects meeting any of the following exclusion criteria must be excluded from participating in the trial:

1. Unwilling or unable to comply with the study protocol.
2. Subjects for who bone metastases are the only available non-target lesions for abscopal effect evaluation.
3. Subjects with tumors for which SBRT is not considered appropriate standard therapy with the exception of subjects with a primary breast tumor. This includes subjects with target lesions less than 1 cm in diameter and those with large central lung lesions.
4. Diagnosis of immunodeficiency or is receiving systemic steroid therapy or any other form of immunosuppressive therapy within 7 days prior to the first dose of trial treatment.
5. Known history of active tuberculosis (Bacillus Tuberculosis).
6. Known or suspected hypersensitivity to pembrolizumab or any of its excipients or any component of the proposed regimen (gene vector/valacyclovir).
7. Known gallbladder or bile duct disease (i.e., infection or cholecystitis) or acute or chronic pancreatitis.
8. ECOG performance status of ≥ 2 or oxygen dependence (e.g., advanced chronic obstructive pulmonary disease).
9. Inability to swallow food or any condition of the upper gastrointestinal tract that precludes administration of oral medications (valacyclovir).
10. Congestive heart failure: New York Association class III or IV heart failure or unstable angina (see Section 12.4).
11. Sustained or clinically significant cardiac arrhythmias including sustained ventricular tachycardia, ventricular fibrillation, clinically significant bradycardia, advanced heart block (Mobitz II or higher atrioventricular nodal block), prolonged corrected QT interval (longer than 470 milliseconds), or history of acute myocardial infarction.
12. Concomitant disease(s) that could prolong QT such as autonomic neuropathy (caused by diabetes or Parkinson's disease), human immunodeficiency virus (HIV), cirrhosis, uncontrolled hypothyroidism, or cardiac failure.
13. History of syncope or family history of idiopathic sudden death.
14. Known additional malignancy that is progressing or requires active treatment. Exceptions include basal cell carcinoma of the skin or squamous cell carcinoma of the skin that has undergone potentially curative therapy or in situ cervical cancer.

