5.2 Trial Treatments

The treatments to be used in this trial is outlined below in Table 2

Table 2 Trial Treatments

Drug	Dose/Potency	Dose Frequency	Route of Administration	Regimen/Treatment Period	Use
ADV/HSV-tk	5 x 10 ¹¹ vp in 2-mL volume	Once	Intratumorally	Day 0	Experimental
Valacyclovir	2 g	t.i.d. for 14 days	Orally	Day 1 - Day 15	Experimental
SBRT*	30 Gy	6 Gy X 5 fractions over 14 days	-	Day 2 - Day 16	Experimental

Drug	Dose/Potency	Dose Frequency	Route of Administration	Regimen/Treatment Period	Use
Pembrolizumab**	200 mg	Q3W	IV infusion	Day 1 of each 3-week cycle	Experimental

vp = viral particles; t.i.d. = three times daily; Q3W = every 3 weeks; IV = intravenous.

*Primary breast tumors will be treated with three-dimensional RT (short course of 5–8 fractions).

**Pembrolizumab will continue until disease progression, unacceptable toxicity, or up to 24 months (35 cycles) in subjects without disease progression. All subjects who stop pembrolizumab treatment with complete response may be eligible for up to an additional 12 months (17 cycles) of pembrolizumab treatment if they progress after stopping pembrolizumab from the initial treatment phase. The subject must meet the conditions outlined in Section 5.2.3.

ADV/HSV-tk

The tumor will be identified by positron emission tomography (PET)/CT by the radiation oncologist. ADV/HSV-tk will be administered intratumorally as a single injection using a 21-gauge needle. For nodal, lung, and liver lesions, ADV/HSV-tk will be administered after fiducial placement for SBRT. For primary lung tumors, ADV/HSV-tk will be administered under endobronchial ultrasound (EBUS) guidance. In cases where the tumor cannot be accessed by EBUS, a CT-guided injection will be performed. For primary breast tumors, ADV/HSV-tk will be administered under ultrasound guidance. For liver and lung metastatic lesions, ultrasound or CT-guided injection of ADV/HSV-tk will be performed. EBUS will be performed with the patient under sedation. Patients will be monitored until the sedation has worn off. For CT-guided injections, local anesthesia will be used and patients will be monitored for several hours after the procedure.

SBRT

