Primary lung tumors and metastatic lesions (breast and lung) will be treated with SBRT (6 Gy X 5 fractions over 2 weeks). Primary breast tumors will be treated with three-dimensional (3D) RT (short course of 5–8 fractions over 2 weeks). Tumor target will be decided by PET/CT scan. For the planned dosing regimen, SBRT simulation will be done before treatment. For subjects with multiple tumors, the largest tumor will be selected. Sedation is not necessary for SBRT.

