5.3.2 Prohibited Concomitant Medications/Therapies

Subjects are prohibited from receiving the following until disease progression is documented per modified irRC and RECIST 1.1:

- Antineoplastic systemic chemotherapy, hormone therapy, or targeted/biological therapy.
- Immunotherapy not specified in this protocol.
- RT not specified in this protocol.

NOTE: Patients are allowed to have palliative radiotherapy to a painful site if they are otherwise benefitting from the trial treatment per the treating physician's judgment and and it is not the target index lesion for tumor response assessment.

- Investigational agents other than pembrolizumab and ADV/HSV-tk.

Live vaccines within 30 days prior to the first dose of trial treatment and while participating in the trial. Examples of live vaccines include, but are not limited to, the following: measles, mumps, rubella, varicella/zoster, yellow fever, rabies, bacillus Calmette-Guérin, and typhoid vaccine.

- Systemic glucocorticoids for any purpose other than to modulate symptoms from an ECI of suspected immunologic etiology. The use of physiologic doses of corticosteroids may be approved after consultation with the Sponsor.

Subjects who, in the assessment by the investigator, require the use of any of the aforementioned treatments for clinical management should be removed from the trial. Subjects may receive other medications that the investigator deems to be medically necessary.

The Exclusion Criteria describes other medications that are prohibited in this trial.

There are no prohibited therapies during the Post-Treatment Follow-up Phase.

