- Overall irPD: $\geq 20\%$ increase in the sum of the longest diameters of target and new measurable lesions (compared to nadir), confirmed by repeat, consecutive observations at least 4 weeks (normally it should be done at 6 weeks) from the date first documented.

Documentation of irPD (based on the modified irRC) does not mandate discontinuation of the study treatment even after irPD is confirmed with CT scan 8 weeks after the initial observation of irPD.

RECIST 1.1 are defined as follows:

Target Lesions (Main Tumor)

- **CR:** Disappearance of all target lesions. Any pathological lymph nodes (whether target or non-target) must have reduction in short axis to < 10 mm.
- **PR:** At least a 30% decrease in the sum of the diameters of target lesions, using the baseline sum diameters as the reference.
- **PD:** At least a 20% increase in the sum of the diameters of target lesions, using the smallest sum on study (includes the baseline sum) as the reference. In addition to the relative 20% increase, the sum must also demonstrate an absolute increase of at least 5 mm. (Note: the appearance of one or more new lesions is also considered progression)
- **SD:** Neither sufficient shrinkage to qualify for PR nor sufficient increase to qualify for PD, using the smallest sum diameters while on study as the reference.

Non-Target Lesions

- **CR:** Disappearance of all non-target lesions and normalization of tumor marker levels. All lymph nodes must be non-pathological in size (< 10 mm short axis).
Note: If tumor markers are initially above the upper normal limit, they must normalize for a patient to be considered in complete clinical response.
- **Non-CR/Non-PD:** Persistence of one or more non-target lesion(s) and/or maintenance of tumor marker levels above the normal limits.
- **PD:** Appearance of one or more new lesions and/or *unequivocal progression* of existing non-target lesions. *Unequivocal progression* should not normally trump target lesion status. It must be representative of overall disease status change, not a single lesion increase.
- Although a clear progression of “non-target” lesions only is exceptional, the opinion of the treating physician should prevail in such circumstances, and the progression status should be confirmed at a later time by the review panel (or investigator).

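### The injected and irradiated lesion can count toward the primary ORR, and no ORR without it is planned, so beating the 19% and 20% nulls would not by itself show enhanced pembrolizumab efficacy

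*Combined protocol and SAP*

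**What the plan says.** The primary endpoint is the ORR of the whole sequence by RECIST 1.1, with modified irRC also documented (sections 3.1 and 4.2.3.1). There is one treatment group and no control (section 1.0).

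- **Which lesion is treated.** Inclusion criterion 4 asks for "a target lesion of suitable diameter (at least 1 cm) for SBRT with the exception of a primary breast tumor, and a non-target lesion" of at least 1 cm. Exclusion criterion 3 uses the same label: "This includes subjects with target lesions less than 1 cm in diameter". Section 5.2 states "For subjects with multiple tumors, the largest tumor will be selected". It also states "For nodal, lung, and liver lesions, ADV/HSV-tk will be administered after fiducial placement for SBRT", so at those sites the irradiated lesion is also the injected one.
- **How response is scored.** Section 7.1.2.7 defines PR as "At least a 30% decrease in the sum of the diameters of target lesions, using the baseline sum diameters as the reference". Its PD definition adds that "the appearance of one or more new lesions is also considered progression", and unequivocal progression of non-target lesions is also PD.
- **What is kept apart.** Section 5.3.2 allows palliative radiotherapy to a painful site only if "it is not the target index lesion for tumor response assessment". The study SBRT has no matching rule.
- **Where untreated disease is examined separately.** Section 3.3 does this only as an exploratory abscopal objective, by CT of a non-target lesion.
- **What is planned.** Section 8.1 sets nulls of 19% (TNBC) and 20% (NSCLC) against 39% and 40%. It lists no ORR that leaves out the treated lesion.

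**The concern.** A lesion that has been injected and given 30 Gy may shrink for purely local reasons. If it sits in the target sum, that shrinkage counts toward the primary endpoint. Section 4.2.1 presents the treatment as an opportunity to enhance pembrolizumab, and the nulls are close to rates reported for PD-1 drugs without local treatment. A reader who sees 39% against 19% will be inclined to conclude that the lead-in made pembrolizumab work better. The same result could come from local control of one lesion with no change in systemic response, and no planned ORR analysis would tell the two apart.

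The wording adds to the problem. In section 5.2, "Tumor target will be decided by PET/CT scan" uses the word in its radiation sense, so target may mean irradiated in one place and RECIST-measured in another. If target means only irradiated, the untreated visceral lesion could itself be a RECIST target and would dilute the local contribution. On either reading, nothing excludes the treated lesion.

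**Working it through.** **1. The plan's own figures (section 8.1).** With p ± 1.96·√(p(1−p)/n):

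- TNBC, 11/28: 39.3% ± 18.1 points, 21.2% to 57.4%.
- NSCLC, 12/29: 41.4% ± 17.9 points, 23.5% to 59.3%.

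Both agree with the plan. The issue is what the endpoint measures, not the arithmetic.

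**2. When local shrinkage alone gives a PR.** Let w be the treated lesion's share of the baseline target sum, and hold the other targets unchanged. The shrinkage needed is 0.30/w. The largest of k targets has w ≥ 1/k (taking largest to mean by diameter), so the need is at most 0.30k.

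| Target lesions | Shrinkage of treated lesion needed for PR |
|---|---|
| 1 | 30% |
| 2 | at most 60% |
| 3 | at most 90% |
| 4, equal size | 120%, impossible alone |

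**3. What the nulls resemble.** The protocol gives 18.5% of 27 TNBC patients responding to pembrolizumab (section 4.2.1) and 19.4% of 495 NSCLC patients (section 4.1.1.4.1). The references cited for the nulls in section 8.1 are, by title, a pembrolizumab TNBC study and a trial of nivolumab against docetaxel in NSCLC. The rates in those two sources cannot be checked from the documents.

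**4. Illustration for TNBC.** The inputs are the section 4.2.1 counts: 5 responders (1 CR, 4 PR) and 7 with SD among 27. Assume a fraction s of the SD patients becomes PR through local effect alone, with everyone else unchanged. Then ORR = (5 + 7s)/27, and the tail probability is exact binomial with n = 28.

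| s | ORR | P(at least 11 of 28) |
|---|---|---|
| 10% | 21.1% | 2.2% |
| 25% | 25.0% | 7% |
| 50% | 31.5% | 24% |
| 75% | 38.0% | 51% |
| null of 19% | 19.0% | 1.0% |

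Reaching 39% would need s = (0.39 × 27 − 5)/7 = 79%.

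Eleven is the plan's illustrative count, not a success rule. It is also the smallest count whose 95% interval by the plan's method lies above 19%: 11/28 has a lower limit of 21.2%, and 10/28 gives 35.7% − 17.7 = 18.0%.

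No SD count is given for NSCLC, so this calculation cannot be repeated there.

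**5. Do the progression rules prevent this?** Under RECIST 1.1 they do so in part: new lesions and unequivocal non-target progression are PD, but stable untreated disease does not block a PR. Modified irRC is weaker. The table in section 12.3 scores a fall of at least 30% in index plus new measurable burden as irPR even when non-index lesions progress unequivocally.

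**The case against.** The strongest reply is that the plan never claims what is being questioned. The endpoint is the ORR of the regimen, local control is part of the rationale in section 4.2.1, and enhancement of pembrolizumab is put only as a possibility. A single-arm trial could not prove enhancement whichever lesions were measured. Each patient must also have a visceral lesion of at least 1 cm for abscopal evaluation, scanned every 8 weeks, and RECIST progression rules bring untreated disease into the primary endpoint. Most of this stands, and it is why all-lesion ORR should remain primary. It does not supply a patient-level response rate for untreated disease, which is the nearest this design can come to its motivating question.

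The illustration also has limits.

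- The conversion fractions have no source in the documents, and at 10% the effect is small.
- The published categories add to 24 of 27 (1 + 4 + 7 + 12). The other three are treated here as non-responders who cannot convert.
- Those patients were heavily pretreated, whereas section 5.1.1 allows at most one prior cytotoxic line for metastatic disease.

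The table shows how the mechanism works. It is not an estimate.

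Finally, an ORR without the largest lesion is not like-for-like with the historical rates. If swelling at the treated site is scored as progression, it could also cancel a response elsewhere. Both points are fair and should be stated beside the result.

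**Conclusion.** The concern holds. Nothing in the plan removes the injected and irradiated lesion from the response sum, and no ORR without it is planned. An ORR above 19% or 20% would describe the regimen's activity but would not by itself show that pembrolizumab worked better.

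The omission is certain; the size of its effect is unknown, because the documents give no local response rate. In TNBC, under the stated assumption and with no systemic gain, the chance of the illustrated 11 of 28 rises from 1.0% at the null to between 2.2% and 51% as the converted share of SD patients goes from 10% to 75%. The effect is largest when the treated lesion is the only target, and local shrinkage alone cannot give a PR with four or more equal targets. This is a cheap improvement to the analysis plan, not a defect in the primary endpoint.

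**What to change.** **Change.**

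- In section 7.1.2.7, state whether the treated lesion belongs to the target sum, and use different terms for the radiation target and the RECIST target.
- Flag the injected or irradiated lesion on the CRF at baseline. The trial is open label, so this should not be left to a later choice.
- Keep all-lesion ORR as primary, with the hypotheses unchanged.
- In section 8.1, prespecify one key supportive analysis, reported beside the primary result and the nulls: ORR on measurable lesions neither injected nor irradiated. Count new lesions or progression at any site as PD, and patients without a measurable untreated lesion as non-responders.
- Report local response of the treated lesion separately.
- Limit any statement about enhanced pembrolizumab efficacy to what the supportive analysis shows.

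**Cost.** A CRF field, a short SAP paragraph and a little more analysis. No extra scans are needed, because CT assessment of an untreated lesion is already scheduled every 8 weeks. If untreated lesions are now recorded only as RECIST non-targets, their diameters must be measured on those scans. Few patients should lack a usable lesion: criterion 4 requires an untreated visceral lesion of at least 1 cm, and section 7.1.2.7 sets 10 mm as the target minimum, though it does so within the modified irRC description. Denominators stay at 28 and 29 and precision does not improve; at 11/28 the half-width is still 18.1 points. The supportive ORR will probably be lower than the all-lesion figure, and its comparison with the historical rates is imperfect because the largest lesion is left out.

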15. Known active central nervous system metastases and/or carcinomatous meningitis. Subjects with previously treated brain metastases may participate provided they are stable (without evidence of progression by imaging for at least 4 weeks prior to the first dose of trial treatment and any neurologic symptoms have returned to baseline), have no evidence of new or enlarging brain metastases, and are not using steroids for at least 7 days prior to trial treatment. This exception does not include carcinomatous meningitis, which is excluded regardless of clinical stability.
16. Active autoimmune disease that has required systemic treatment in the past 2 years (i.e., with use of disease modifying agents, corticosteroids or immunosuppressive drugs). Replacement therapy (e.g., thyroxine, insulin, or physiologic corticosteroid

- replacement therapy for adrenal or pituitary insufficiency, etc.) is not considered a form of systemic treatment.
17. History of (non-infectious) pneumonitis that required steroids or current pneumonitis.
 18. Active infection requiring systemic therapy.
 19. History or current evidence of any condition, therapy, or laboratory abnormality that might confound the results of the trial, interfere with the subject's participation for the full duration of the trial, or is not in the best interest of the subject to participate, in the opinion of the treating investigator.
 20. Known psychiatric or substance abuse disorders that would interfere with cooperation with the requirements of the trial.
 21. Pregnant or breastfeeding, expecting to conceive or father children within the projected duration of the trial, starting with the prescreening or screening visit through 120 days after the last dose of trial treatment, or is unwilling to practice an effective method of birth control. Women of childbearing potential must have a negative serum pregnancy test within 7 days prior to administration of trial treatment.
 22. Prior treatment with gene vector therapy.
 23. Prior treatment with immunomodulatory therapy or immunotherapy (TNBC cohort only)
 24. Prior treatment with an anti-PD-1, anti-PD-L1, or anti-PD-L2 agent (TNBC cohort only).
 25. Known history of HIV (HIV 1/2 antibodies).
 26. History of liver disease such as cirrhosis or known active hepatitis B (e.g., hepatitis B surface antigen reactive) or hepatitis C (e.g., hepatitis C virus RNA [qualitative] is detected).
 27. History of or current alcohol misuse/abuse within the past 12 months.

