In both the TNBC and NSCLC cohorts, ADV/HSV-tk dose will be de-escalated to 5×10^9 vp if unacceptable toxicity occurs with the planned dose of ADV/HSV-tk. If toxicity occurs with this dose modification, the dose will be further de-escalated to 5×10^6 vp.

Dosing interruptions for pembrolizumab and SBRT/3D RT are permitted in the case of medical/surgical events or logistical reasons not related to study therapy (e.g., elective surgery, unrelated medical events, patient vacation, and/or holidays). Subjects should be placed back on study therapy within 3 weeks of the scheduled interruption, unless otherwise discussed with the Sponsor. The reason for interruption should be documented in the patient's study record. Patients whose treatment is interrupted or permanently discontinued due to an AE including abnormal laboratory value must be followed at least once a week for 4 weeks and subsequently at 4-week intervals until resolution or stabilization of the event, whichever comes first. Dose interruptions should be reported on the appropriate Dosage Administration case report form (CRF). The maximum time allowed for toxicity-related treatment interruption is 21 days (3 weeks) from the intended dosing day. If interruption is > 3 weeks, the patient must be discontinued from the study treatment. However, the patient will continue to be followed for toxicity.

Valacyclovir: For patients with serum creatinine level of $1.6\text{--}2.0 \times \text{ULN}$, valacyclovir dose will be reduced 50% (i.e., 1 g t.i.d.).

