5.2.2 Timing of Dose Administration

All trial treatments will be administered on an outpatient basis.

ADV/HSV-tk (5×10^{11} vp) in a 2-mL total volume will be injected intratumorally on Day 0 of the study. For nodal, lung, and liver lesions, ADV/HSV-tk will be administered after fiducial placement for SBRT.

Valacyclovir will be orally administered at a dose of 2 g t.i.d. for 14 days from Day 1 to Day 15 of the study.

Primary lung tumors and metastatic lesions (breast and lung) will be treated with SBRT (30 Gy; 6 Gy X 5 fractions). Primary breast tumors will be treated with a short course (5–8 fractions) of 3D RT. SBRT and 3D RT will be administered over 2 weeks from Day 2 to Day 16 of the study.

Pembrolizumab 200 mg will be administered as a 30 minute IV infusion Q3W (\pm 1 day). Sites should make every effort to target infusion timing to be as close to 30 minutes as possible. However, given the variability of infusion pumps from site to site, a window of -5 minutes and +10 minutes is permitted (i.e., infusion time is 30 minutes: -5 min/+10 min).

The Pharmacy Manual contains specific instructions for the preparation of the pembrolizumab infusion fluid and administration of infusion solution.

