If a dose of pembrolizumab meeting the protocol definition of overdose is taken without any associated clinical symptoms or abnormal laboratory results, the overdose is reported as a non-serious ECI, using the terminology “accidental or intentional overdose without adverse effect.”

For valacyclovir overdose, activated charcoal may be administered to aid in the removal of unabsorbed drug. General supportive measures are recommended. Acute renal failure and neurological symptoms, including confusion, hallucinations, agitation, decreased consciousness and coma, and nausea and vomiting may occur. Caution is required to prevent inadvertent overdose. Many of the reported cases involved renally impaired and geriatric patients receiving repeated overdoses due to lack of appropriate dosage reduction.

All reports of overdose with and without an AE must be reported within 24 hours to the Sponsor ([contact]; [contact]) and within 2 working days hours to Merck Global Safety (Attn: Worldwide Product Safety; [contact]).

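### Table 1's albumin entry limit is printed in mg/dL and so excludes no one as written; its creatinine-clearance footnote feeds no rule and needs a sponsor answer

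*Combined protocol and SAP*

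**What the plan says.** **Albumin.** Inclusion criterion 7 (Section 5.1.2) requires adequate organ function as defined in Table 1. The albumin row requires at least 2.5 mg/dL. The hemoglobin row of the same table is in g/dL (at least 8). No other section states an albumin limit.

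**Renal entry.** The only row under the renal heading of Table 1 is serum creatinine, at "<2 X upper limit of normal (ULN"). A footnote to the table adds that "CrCl should be calculated per institutional standard". No exclusion criterion in Section 5.1.3 names renal impairment. The age criterion sets a minimum of 18 "years of age on the day of informed consent signing" and no maximum.

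**Valacyclovir.** Section 5.2.2 states: "Valacyclovir will be orally administered at a dose of 2 g t.i.d. for 14 days". The only renal adjustment is in Section 5.2.1.2. It begins "For patients with serum creatinine level of" 1.6 to 2.0 times ULN, and for those patients the "valacyclovir dose will be reduced 50% (i.e., 1 g t.i.d").

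**Caution.** The overdose text in Section 7.2.1 says of valacyclovir: "Many of the reported cases involved renally impaired and geriatric patients receiving repeated overdoses due to lack of appropriate dosage reduction".

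**The concern.** A laboratory entry limit should separate patients who may enter from those who may not. A limit of 0.0025 g/dL separates nobody. Anyone auditing eligibility against the text would have to find every patient compliant on albumin, whatever limit the sponsor had in mind. Section 5.2.3 also applies the safety parameters of the inclusion criteria to patients returning for a second course of pembrolizumab, so the slip carries over to that point.

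The renal material raises a question of a different kind. The table mentions CrCl, but nothing in the protocol acts on it. The valacyclovir rule looks only at serum creatinine, which takes no account of age or weight, while the overdose text singles out renally impaired and geriatric patients whose dose was not suitably reduced. Either the footnote is left over from a template, or a clearance-based rule was intended and is missing. The text does not show which.

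**Working it through.** The plan gives no derived figure on this point to reproduce. The check is a unit conversion, a text comparison and one illustration.

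**1. Albumin unit.** Input: 2.5 mg/dL (Table 1).
- 2.5 mg/dL ÷ 1,000 mg per g = 0.0025 g/dL.
- If g/dL was meant, the limit is 2.5 × 1,000 = 2,500 mg/dL, which is 1,000 times the printed value.
- Example: an albumin of 2.0 g/dL is 2,000 mg/dL. It passes the printed limit 800-fold (2,000 ÷ 2.5) but fails a limit of 2.5 g/dL.

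**2. Where CrCl is used.**

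| Place | Renal measure used |
|---|---|
| Table 1, renal row | Serum creatinine, below 2 × ULN |
| Table 1, footnote | CrCl named, no limit attached |
| Section 5.1.3, exclusions | None |
| Section 5.2.1.2, valacyclovir dose | Serum creatinine, 1.6–2.0 × ULN |
| Section 7.1.3, Table 5 laboratory list | Creatinine listed, CrCl not listed |
| Section 7.2.1, overdose | Renal impairment and older age named, no measure |

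The footnote is the only place where CrCl appears.

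**3. What the dosing rule does.**
- Full dose: 2 g × 3 = 6 g/day; × 14 days = 84 g.
- Reduced dose: 1 g × 3 = 3 g/day; × 14 days = 42 g.
- A patient below 1.6 × ULN takes the full 84 g whatever the clearance.

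**4. Illustration of why the question is worth asking.** The documents give no ULN, age or weight, so these are assumptions. Take a woman of 75 years and 55 kg, a standard age-weight-creatinine formula, and a ULN of 1.0 mg/dL:
- CrCl = (140 − age) × weight × 0.85 ÷ (72 × creatinine)
- Creatinine at 1.0 × ULN: 65 × 55 × 0.85 ÷ 72 = 42.2 mL/min.
- Creatinine at 1.5 × ULN: 42.2 ÷ 1.5 = 28.1 mL/min.

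Over an assumed ULN of 0.8 to 1.3 mg/dL, the results run from 53 down to 32 mL/min at 1.0 × ULN, and from 35 down to 22 mL/min at 1.5 × ULN. In every case she meets the renal entry limit and takes the full dose. This shows only that creatinine multiples and clearance can rank patients differently. It does not show that her dose is wrong, because the documents give no clearance cut-off for valacyclovir.

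**The case against.** The case against making much of this is fair, and a good part of it stands.

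On albumin, a clinician would recognise the unit as a slip and apply 2.5 g/dL. Wrong enrolment is therefore unlikely, and the factor of 1,000 measures the misprint rather than any effect on patients. That limits the consequence. It does not make the printed criterion correct.

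On the footnote, the table was read from a PDF, and a reference marker could have been lost in that step, so the absence of a marker proves nothing. The creatinine row nevertheless reads as complete, and the valacyclovir rule stands in running text that uses creatinine alone.

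On dosing, the protocol has both a renal entry limit and a renal dose reduction, so it does respond to the hazard that Section 7.2.1 describes. Section 4.2.2 cites a previous trial that used the same regimen. Exclusion 19 lets the investigator turn away a patient for whom it "is not in the best interest of the subject to participate, in the opinion of the treating investigator", although it names no renal measure and sets no dose. Choosing clearance over creatinine is a clinical judgement. This argument stands, and it is why the renal part is a query.

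**Conclusion.** The albumin criterion is wrong as written: at 0.0025 g/dL it excludes no one. The size is a factor of 1,000 in the text and probably close to nil at the bedside. The only assumption is that g/dL was meant, which the sponsor should confirm.

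The unused CrCl footnote and the creatinine-only valacyclovir rule are a secondary query. Neither part touches the response-rate endpoint, the sample size or the analysis.

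A reader might infer three stronger things, which the documents do not support:

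- **That the creatinine rule is wrong and patients will be overdosed.** This would need a clearance threshold, and the documents give none. The illustrative clearances rest on an assumed patient and ULN.
- **That renal or neurological toxicity could stop the safety run-in.** The only definition of toxicity, in Section 3.2 (objective 4), is treatment-related death or hematological toxicity of Grade 3 or higher. Section 8.1 uses the word without redefining it. On that definition, non-fatal renal or neurological events do not count.
- **That valacyclovir toxicity would be wrongly charged to the combination.** Table 2 lists valacyclovir as an experimental treatment, and Section 3.2 names it within the regimen whose toxicity is studied. Attributing its toxicity to the regimen is correct.

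**What to change.** **Correction.** In Table 1, change the albumin unit from mg/dL to g/dL, so that the row reads 2.5 g/dL or more, after the sponsor confirms the value. The cost is one unit in the next amendment. No test is added, and no patient is handled differently at sites that already read the limit as g/dL.

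**Query.** Ask the sponsor's clinical team whether a CrCl rule was intended for valacyclovir. If not, delete the footnote. If so, the team should state the rule in Section 5.2.1.2 and attach the footnote to the place where it applies. Deletion costs one line. A clearance rule would need an agreed threshold, which is for the clinicians to set, but no new laboratory test: creatinine and weight are already measured at screening, and age is needed for eligibility. A few patients might then be dosed differently.
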